## 2.9 Clinical Studies

HPTN 050, also known as Phase I Safety and Acceptability Study of the Vaginal Microbicide Agent PMPA Gel is the most recently published study of tenofovir vaginal gel. Eighty-four (60 HIV-uninfected and 24 HIV-infected) women applied either 0.3% or 1% tenofovir gel once or twice daily. Both of the tenofovir gel formulations were well tolerated in both HIV-uninfected and HIV-infected women. Although 91% reported at least one AE, the majority (88%) were mild and limited to the GU tract. Product concentration, sexual activity and HIV status were not associated with a specific AE pattern. No clinically significant systemic toxicity was observed. Tenofovir gel showed no negative effect on vaginal microflora in this study. No new resistance mutations were detected in plasma or cervicovaginal lavage after 14 days of tenofovir gel use but three women had plasma mutations associated with low level tenofovir resistance at day 0 and 14 (M41L, L210M,  $\pm$ T215I/Y). Systemic absorption was limited (maximum serum levels 3.1-25.8 ng/ml). The AE and safety profile in HPTN 050 was reviewed recently by the FDA during their review of the HPTN-059 extended safety protocol for vaginal tenofovir.

A male tolerance study of tenofovir 1% vaginal gel (CONRAD A04-099) was recently completed, and is currently in the analysis stage.

Several other tenofovir 1% vaginal gel studies are ongoing or in development. These include:

- HPTN 059: Phase II Expanded Safety and Acceptability Study of the Vaginal Microbicide 1% Tenofovir Gel
- CONRAD A04-095: Single Dose and 14-Day Once or Twice-daily Pharmacokinetic Study of the Vaginal Microbicide Agent 1% Tenofovir Gel
- CAPRISA 004: Safety and Effectiveness Study of a Candidate Vaginal Microbicide for Prevention of HIV (Phase IIb, two-arm, double-blinded, randomized, placebo controlled trial comparing coitally dependent 1% tenofovir gel with a placebo gel)
- MTN-001: Phase II Adherence and Pharmacokinetics Study of Oral and Vaginal Preparations of Tenofovir
- MTN-003: Phase 2B Safety and Effectiveness Study of Tenofovir 1% Gel, Tenofovir Disoproxil Fumarate (DF) Tablet and Tenofovir DF-Emtricitabine Tablet for the Prevention of HIV-1 Infection in Women
- MTN-007: Phase I Rectal Safety of Tenofovir Gel

## 2.10 Vaginal Gel Pharmacokinetics

[figure not shown]
Limited vaginal pharmacokinetic data in primates and humans demonstrate that tenofovir gel is broadly distributed in vaginal tissues following vaginal application and can penetrate to epithelial tissues. The amount of tenofovir administered by intravaginal application of 4 grams of a 1% dose is 40 mg. This dose of tenofovir is slightly more than half the amount absorbed following oral ingestion (approximately 25% or 75 mg) of a 300 mg tablet of TDF.

Tenofovir (0.3% and 1%) gel was recently tested in the HPTN 050 Phase I study. In this trial, tenofovir gel was administered intravaginally in four groups of women: sexually abstinent HIV-uninfected and HIV infected women, and sexually active HIV-uninfected and HIV-infected women. The women and their male partners (in the sexually active cohorts) were also asked to assess the acceptability of the product. Results from the HPTN 050 Phase I study have shown tenofovir 1% gel to be safe and acceptable. In light of the favorable findings, an expanded safety and tolerability study of tenofovir gel is underway (HPTN 059).

HPTN 050 also addressed pharmacokinetics of vaginally administered tenofovir gel. Fourteen of 25 women (56%) with pharmacokinetic results had low, but detectable, serum tenofovir levels (limit of quantitation: 3.0 ng/mL) at some point in the 12 hours after dosing on either Day 0 (following the first dose) or on Day 13 (after daily dosing); three of the 14 had detectable levels on both days. The maximum tenofovir concentrations ( $C_{max}$ ) ranged from 3.0 - 25.8 ng/mL, with no clear dose-concentration relationship identified. For the woman with the 25.8 ng/mL level, this peak level occurred two hours following the dose; the level rapidly declined to 10.9 ng/mL at four hours and was undetectable at 12 hours following the dose. Besides the outlier with the highest tenofovir level, the next highest  $C_{max}$  was 7.1 ng/mL. Considering all women in the PK cohort, the median tenofovir  $C_{max}$  was 3.4 ng/mL (interquartile range: below limit of quantitation [3.0 ng/mL] to 4.7 ng/mL). The median  $C_{max}$  for all subjects (3.4 ng/mL) corresponds to approximately 1% of the maximum ( $C_{max, steady-state (ss)}$ ) and 7% of the minimum (C24 single dose) blood concentrations at steady-state with 300 mg daily oral tenofovir dosing. Findings from CONRAD A04-095 are expected to further inform the pharmacokinetic data on vaginally administered tenofovir gel.

Figure 1 presented below demonstrates tenofovir blood concentration following vaginal administration of tenofovir 1% gel in HPTN 050. All levels for all women with measurable tenofovir levels in the blood are shown. (14 of 25; lower limit of quantitation (LLOQ) approximately 3.0 ng/mL [dotted line]). Legend indicates “cohort” – “ID” – “study day”. For reference the tenofovir level associated with the median 24 hour post-dose blood concentration following an oral 300 mg tenofovir dose is indicated with dashed line.

**Figure 1 - Tenofovir Blood Concentrations vs. Time after Vaginal Administration**

First letter = Cohort

Cohort A - HIV -uninfected/sexually abstinent

Cohort B - HIV -uninfected/sexually active

Cohort C - HIV-infected/sexually abstinent

Cohort D - HIV-infected/sexually active

4 digits = last 4 digits of participant identifier

Last digit = day of study

The current study will expand the ongoing evaluation of tenofovir gel into the term pregnant population. It is conceivable that the absorption and pharmacokinetics of tenofovir gel in the 3rd trimester of pregnancy may differ from the non-pregnant data above, given increased blood flow to the pelvic tissues and engorgement of the pelvic vessels. With hypothesized increased absorption from the pelvic tissues, the potential for placental transfer exists. This protocol will also evaluate that endpoint.

The validated LCMS (liquid chromatography mass spectrometry) method planned for MTN-002 has a limit of quantitation (LOQ) of 5 ng/mL, but uses only 50 microliters of fluid. Previous methods have had a LOQ of 3 ng/mL but used 250 microliters. Since assay sensitivity is largely determined by mass in the sample, not concentration, this likely represents a 3 fold improvement in sensitivity if we use a similar volume as in previous studies. To improve even further, we are planning to dedicate 1 mL serum for the blood tenofovir assay to further increase the sensitivity, possibly below 1 ng/mL. This may increase the number of samples quantifiable in the blood assuming similar pharmacokinetics as in HPTN 050.

No PK analysis is planned beyond description of  $C_{max}$  and  $T_{max}$ . Estimates of vaginal absorption, systemic clearance, volume of distribution, and half-life require accurate assessment of the initial rise in concentration, area under the concentration time curve (AUC), and terminal elimination slope. Since only the concentration at 1 – 3 time points near  $C_{max}$  in only some women (based on HPTN 050 experience) may be expected to be measurable, data from this study cannot be used to estimate initial absorption, AUC, or terminal elimination slope.

## 2.11 Study Hypothesis

We hypothesize that:

- Plasma absorption in participants will be detectable in a percentage of women similar to that seen in HPTN 050 (approximately 33%)
- Of women with detectable levels of tenofovir, a small fraction will have detectable levels in endometrium, cord blood, placental tissue, and amniotic fluid

## 2.12 Justification of Dosing

Choice of the tenofovir 1% gel concentration for MTN-002 is based on both animal and clinical evidence suggesting an appropriate safety profile and potency. Animal and human studies have demonstrated minimal vaginal irritation at this concentration. A rabbit vaginal irritation test identified tenofovir 1% gel as being histopathologically identical to sham or control treatment, while on a qualitative basis 3% gel was more irritating to vaginal epithelia. The tolerability of the 1% gel was confirmed in the HPTN 050 Phase I study, the Phase I dose ranging study of tenofovir gel (0.3% once daily, then 1% once daily, then 0.3% twice daily followed by 1% twice daily). In this study, of the two doses and frequencies studied in the dose finding cohort, the 1% gel applied intravaginally twice daily for 14 days was well tolerated and was identified as the highest practical dose and frequency for further study in subsequent cohorts.

The second line of evidence is from vaginal transmission inhibition studies performed in non-human primates. Six separate studies provided evidence for efficacy of the gel over a range of tenofovir concentrations of 0.3% to 10%. Although the total data are limited and a powered statistical determination as to the efficacy of 1% tenofovir gel versus 0.3% and 10% cannot be made, empirical examination of the efficacy data identifies tenofovir 1% gel as the lowest efficacious concentration tested when given within two hours of infection.

Finally, the amount of tenofovir administered by intravaginal application of 4 grams of a 1% dose (40 mg) is similar to the orally absorbed amount that has been shown to be highly active against HIV and results in a reduction of plasma HIV RNA of 1.5 log10 copies/mL after daily administration for 21 days. Comparison of the predicted cervicovaginal concentrations of tenofovir gel delivered to those achieved systemically at the standard treatment dose of 300 mg oral TDF, and tenofovir's characteristic prolonged intracellular half-life (diphosphate form, nine to 50 hours depending upon cell type), suggest that an initial and potentially durable barrier to HIV transmission may be possible. In terms of weighing potential risks and benefits, the 1% tenofovir gel minimizes the potential risks of vaginal epithelial toxicity while providing the potential benefit of delivering sufficient tenofovir to achieve an initial and possibly durable barrier to infection.

## 3 OBJECTIVES

### 3.1 Primary Objectives

- Assess term pregnancy maternal single-dose pharmacokinetics of tenofovir 1% vaginal gel

### 3.2 Secondary Objectives

- Characterize the systemic safety profile of single-dose tenofovir 1% vaginal gel in term gravidas
- Compare 3rd trimester absorption of tenofovir 1% vaginal gel to absorption in non-pregnant recent historic controls
- Assess amniotic fluid, cord blood, endometrial tissue and placental tissue levels following single-dose tenofovir 1% vaginal gel

## 4 STUDY DESIGN

### 4.1 Identification of Study Design

MTN-002 will be a Phase I, single-site, open label investigation into the single-dose pharmacokinetic parameters and placental transfer of tenofovir gel when administered to term gravidas scheduled for elective cesarean section. We will enroll 16 healthy HIV-uninfected women, obtain baseline blood samples, place the gel in the vagina with a target administration time approximately two hours prior to the expected time of cesarean section (optimally a minimum of one hour prior to the collection of cord blood), and then obtain blood samples at the following times: 1, 2, 4, 6, 8, 12 and 24 hours following gel placement. In addition, amniotic fluid, placenta, and endometrial specimens will be collected.

### 4.2 Summary of Major Endpoints

- Maternal 3rd trimester pharmacokinetic measures (AUC, Cmax,)
- Endometrial tenofovir levels
- Placental transfer (cord blood tenofovir levels, placental tissue tenofovir levels, amniotic fluid tenofovir levels)

### **4.3 Description of Study Population**

The study population will consist of 16 pregnant women aged 18-45 who are healthy, non-HIV infected and at term. The gravidas will be expected to be scheduled for elective cesarean section (CS) at  $\geq 37$  and  $< 42$  completed gestational weeks and will lack evidence of placental disease (no hypertension, diabetes mellitus, collagen vascular disease, placental abruption, etc.) as described in Section 5.3.

### **4.4 Time to Complete Enrollment**

Time to complete study enrollment is expected to be approximately eighteen months.

### **4.5 Study Group**

A single study arm is planned. A total of approximately 16 women will be enrolled. Additional participants will be enrolled to ensure that a total of 16 evaluable participants complete the study.

The following types of participants will be replaced:

- Participants who are enrolled but do not receive study gel
- Participants who receive study gel but whose time of cesarean delivery is greater than 8 hours following the time of study gel administration

### **4.6 Sequence and Duration of Trial Periods**

Acknowledging that it is not always possible to complete study evaluations/visits on the targeted dates/times, evaluations/visits may be completed within a specified window around the target date/time.

The time of cesarean section may be changed for clinical, administrative, or other reasons outside the control of the study staff. Gel administration that occurs outside the specified window due to such changes will not be considered a protocol violation.

**Table 1: Visit Windows**

Visit	Screening and Enrollment	Gel Administration	0-12 hr PK	24 Hour Evaluation	Two Week Phone Call
Window	Up to four weeks prior to expected date of gel administration (Day 0) and with reasonable allowance for turn-around-time of laboratory analyses drawn at Screening and Enrollment	Up to four hours prior to the expected time of cesarean section, with an optimal minimum of one hour prior to the expected time of cord blood collection	15 minutes +/- scheduled blood draw	22 – 26 hours	Day 10 – Day 18
Target	No target	Defined as Day 0, Time 0  2 hours prior to expected time of cesarean delivery	1, 2, 4, 6, 8, 12 hours following gel placement	24 hours following gel placement	Day 14

#### 4.7 Expected Duration of Participation

The expected duration of participation for individual enrolled participants will depend on how long they enroll prior to the date of cesarean section, but may range from approximately three to six weeks. Participants who have Adverse Events (AEs) which are not resolved at the Two Week Phone Call will be followed beyond this point using Unscheduled Visits as necessary until a clinically acceptable resolution of the AE(s) (at the discretion of the Site Principal Investigator (PI) or NIH (Medical Monitors) has been documented, including resolution date, if possible. No further study data (for purposes of data analysis) will be collected for these participants after the Two Week Phone Call.

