## 7.5 Two Week Phone Call

The Two Week Phone Call will collect data on any new or outstanding adverse events, as well as other procedures as outlined in Table 5. The window for the phone call is Day 10 to Day 18.

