**Table 5: Two Week Phone Call**

Two Week Phone Call	
Component	Procedure/Analysis
Administrative	
 
• Update locator information
 
• Update demographics
 
• *Review inpatient chart
 
• *Review outpatient chart
 
• Trigger staff to send reimbursement for phone call
 
• *Schedule next visit
 

Clinical	
 
• Update concomitant medications
 
• Update adverse events
 

\*as clinically indicated

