## 7.7 Final Contact

In most cases the final contact will be the Two Week Phone Call. If necessary, the study site may complete the final contact visit(s), including the script for the Two Week Phone Call, at the study site or at community based locations, depending on site

capacities and site and participant preferences. All final contacts must be documented in participant study records.

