### **8.3 Adverse Events Definitions and Reporting Requirements**

#### **8.3.1 Adverse Events**

An AE is defined as any untoward medical occurrence in a clinical research participant administered an investigational product and which does not necessarily have a causal relationship with the investigational product. As such, an AE can be an unfavorable or unintended sign (including an abnormal laboratory finding, for example), symptom or disease temporally associated with the use of an investigational product, whether or not considered related to the product. The term “investigational product” for this study refers to tenofovir gel.

Study participants will be instructed to contact the study site staff to report any AEs they may experience, except for life-threatening events, for which they will be instructed to seek immediate emergency care. Where feasible and medically appropriate, participants will be encouraged to seek medical care where the study clinician is based, and to request that the clinician be contacted upon their arrival. With appropriate permission of the participant, and whenever possible, records from all non-study medical providers related to AEs will be obtained and required data elements will be recorded on study case report forms. All participants reporting an AE (including pelvic exam abnormalities) will be followed clinically until the AE resolves (returns to baseline) or stabilizes.

Study site staff will document on study CRFs all AEs reported by or observed in enrolled study participants from the time of enrollment until study termination, regardless of severity and presumed relationship to study product. The Protocol Specific Toxicity

Table (Appendix V) will be the primary tool for grading adverse events for this protocol, with the exception of asymptomatic bacterial vaginosis which will not be a reportable AE. Adverse events not included in that table will be graded by the DAIDS AE Grading Table Version 1.0, December 2004. In cases where an AE is covered in both tables, the Protocol Specific Toxicity Table will be the grading scale utilized.

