# **10 STATISTICAL CONSIDERATIONS**

## **10.1 Overview and General Design**

This is a single-dose, single-site, open label study. All the enrolled women will be administered tenofovir 1% vaginal gel. The planned total length of follow-up is 2 weeks.

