## **10.5 Participant Accrual, Follow-up, and Retention**

The accrual period will be 18 months. The study site will recruit and enroll a total of 16 participants. Each participant will be followed for two weeks following gel administration. Once a participant has enrolled in the study, the study site will make every reasonable effort to retain her for the entire study period.

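### After 24 hours the mother's inpatient chart need not be reviewed, and the final grade and outcome of adverse events still open at the phone call stay out of the analysis

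*Protocol*

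**What the plan says.** **Schedule.** Inpatient chart review is a required item at the 24 Hour Evaluation (Table 4), which takes place 22 to 26 hours after gel. The next scheduled contact is the phone call: "The Two Week Phone Call will collect data on any new or outstanding adverse events". Table 1 gives it a Day 14 target, and Section 7.5 states: "The window for the phone call is Day 10 to Day 18". Section 7.7 adds: "In most cases the final contact will be the Two Week Phone Call". In Table 5 the item "Review inpatient chart" carries the asterisk that makes it conditional on clinical indication, and Appendix I gives it the matching triangle symbol.

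**Grading.** Section 8.3.1 makes Appendix V the primary grading tool. For postpartum endometritis, Appendix V separates Grade 2 from Grade 3 mainly by whether parenteral antibiotics lasted up to 3 days or longer. For postpartum hemorrhage after cesarean it uses estimated blood loss (1000 and 1500 cc cut points) and units transfused (1–2, or more than 2).

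**Data after the call.** Section 4.7 sends women with unresolved adverse events to Unscheduled Visits until an acceptable resolution is documented, with its date if possible. It then says: "No further study data (for purposes of data analysis) will be collected for these participants after the Two Week Phone Call". Section 8.3.1 has all adverse events entered on case report forms from enrollment to study termination, and says that participants with an event "will be followed clinically until the AE resolves (returns to baseline) or stabilizes".

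**The concern.** Characterizing systemic safety is a listed secondary objective (Section 3.2). Appendix I schedules no creatinine, AST or ALT after dosing; these tests appear later only as optional items at an Unscheduled Visit. Beyond the first day, the safety description therefore rests on adverse event reports.

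Two features weaken those reports. First, every participant is an inpatient recovering from a cesarean, so a hospital record exists for each. The protocol nevertheless stops requiring anyone to read it at about 24 hours. Later inpatient events then depend on what the woman reports, or on someone judging that a chart review is indicated.

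Second, the closing sentence of Section 4.7 applies only to women whose events are still open at the call. They have the longest-lasting events, and they are the only ones for whom the protocol plans continued follow-up. Examinations and laboratory tests at their Unscheduled Visits (Table 6) could show a higher grade or settle the outcome, and that information would not be analysed.

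**Working it through.** **1. Reproduce the stated duration.** Section 7.1 gives about 1 to 4 weeks from enrollment to cesarean. Sections 10.1 and 10.5 give 2 weeks of follow-up. 1 + 2 = 3 and 4 + 2 = 6 weeks, which matches the 3 to 6 weeks in Section 4.7. The two-week figure is thus the Day 14 target.

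**2. Interval without a scheduled safety observation.** The last required contact before the call is at 22 to 26 hours.
- Shortest gap: 10 − 26/24 = 8.9 days.
- On target: 14 − 24/24 = 13.0 days.
- Longest gap: 18 − 22/24 = 17.1 days.

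This holds for all 16 women. It concerns scheduled observation only; participant-initiated contact and Unscheduled Visits remain possible.

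**3. Can the 24-hour chart review supply the Appendix V grade?** Postpartum endometritis follows delivery, and delivery follows gel, so antibiotics for it start after Time 0.
- With a day as 24 hours, the Grade 2/3 antibiotic boundary falls no earlier than 3 × 24 = 72 hours after gel. The latest required chart review is at 26 hours: 72 − 26 = 46 hours too early.
- If delivery occurs at the 2-hour target and treatment starts at once, the boundary is at 2 + 72 = 74 hours: 74 − 26 = 48 hours too early.
- If days are counted as calendar days, entering a fourth day takes more than 48 hours: 48 − 26 = 22 hours too early.

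Under each reading the antibiotic criterion cannot be settled by the last required review. Blood loss at surgery will usually be in the chart by 24 hours, so for hemorrhage the gap concerns later bleeding and later transfusion. Those too are chart facts that a woman is poorly placed to state by phone 10 to 18 days afterwards.

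**4. Sections 4.7 and 8.3.1 side by side, for an event open at the call.**

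| Item | Section 4.7 | Section 8.3.1 |
|---|---|---|
| Clinical follow-up | Continues to acceptable resolution | Continues until resolved or stable |
| Documentation | Resolution, with date if possible | Case report forms until study termination |
| Use in analysis after the call | Excluded | Not addressed |

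The sections agree on follow-up. They leave unclear whether a later grade or outcome is case report form data for analysis. The protocol text shown does not define study termination for a woman followed past the call. Section 7.7 makes the call the last contact only in most cases, so a later end of participation is possible.

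**5. Direction.** A maximum grade taken up to the call cannot exceed the maximum over the whole event, so the cut-off can only leave the reported grade equal or lower. It does not change the count of events already recorded. An inpatient event never mentioned at the call would be missing from the count. The documents give no adverse event onset or duration data, so neither effect can be sized.

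**The case against.** The strongest reply is that safeguards exist. Participants are told to contact staff about any event, outside records are sought where possible (Section 8.3.1), and Unscheduled Visits are available. A reported fever or transfusion would be an obvious reason to open the chart, and Appendix I has the records release obtained again at discharge if possible. New and outstanding events must be asked about at the call, and expedited reporting runs throughout participation. All of this stands and limits the damage. But these routes mostly start from someone noticing or reporting an event, and none makes the chart a source for every woman.

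On Section 4.7, it can be said that one rule governs clinical follow-up and the other the data cut, and that tabulating ongoing events belongs in an analysis plan. The first part is fair. The exclusion, however, is written into the protocol itself, so it is not detail left to a later document.

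Two stronger readings are tempting, and the documents support neither.
- A reader might infer that the promised follow-up is not delivered, because Section 10.5 says "Each participant will be followed for two weeks following gel administration" and Section 10.1 says "The planned total length of follow-up is 2 weeks", while the call may fall on Day 10. The window is symmetric: 14 − 10 = 4 days short at one edge (4/14 = 28.6%) and 18 − 14 = 4 days over at the other. Two weeks is met on target. This is an ordinary visit window and does not by itself bias reporting one way.
- A reader might infer that unresolved events lose their outcome. Section 4.7 requires the resolution to be documented, so the outcome is missing from the analysis but not from the record.

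**Conclusion.** Two narrow points hold. Required chart review ends at 22 to 26 hours, although the protocol's own grading of postpartum endometritis depends on treatment duration that cannot be known until at least 22 hours later by calendar-day counting, or 46 hours later by 24-hour days. Also, read literally, Section 4.7 keeps post-call grade changes and outcomes out of the analysis for just those women with unresolved events, and this is not reconciled with Section 8.3.1.

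The consequence is confined to a secondary, descriptive safety objective in about 16 women. The pharmacokinetic and placental endpoints, with scheduled sampling complete by the 24 Hour Evaluation, are untouched, and no adverse event rate enters the sample size. Any effect on recorded severity is downward or nil. Its size is unknown, because the documents give no data on event timing or on how often indicated chart reviews would take place. The verdict assumes that Section 4.7 is applied as written and that chart review is not done routinely where the protocol makes it conditional. The point is worth correcting mainly because correction is cheap.

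**What to change.** 1. In Table 5 and Appendix I, make review of the mother's inpatient chart through discharge a required item for every woman, completed by the time of the call.
2. Replace the last sentence of Section 4.7 and align it with Section 8.3.1: for adverse events with onset by the call, maximum grade, outcome and resolution date are recorded on the case report form and included in the safety summary. Adverse events with later onset are listed separately.
3. Keep the Day 10 to 18 window. Moving the call to Day 14 to 18 would lengthen recall and cut the window from nine calendar days to five, a trade-off this point does not justify.

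**Cost.** Wording changes to the protocol and case report form, one chart review per woman (about 16 in all) at a single hospital, and a possibly later data close for a woman whose event is still ongoing.
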